## 2.2 Secondary Endpoints

To evaluate the following overall and for individual readers for:

1. the partial ROC AUC corresponding to 95-99% sensitivity with specificities extrapolated from the respective Imagio and IUS ROC curves as applicable.
  - the observed and model-adjusted specificity and sensitivity
  - the Negative Likelihood Ratio (NLR) defined as  $((1-\text{sensitivity})/\text{specificity})$
  - the upgrade and downgrade metrics:
    - the percent correct of downgrades for benign masses from IUS BI-RADS 4a to Imagio (IUS+OA) BI-RADS 2-3, and from IUS BI-RADS 3 to Imagio (IUS+OA) BI-RADS 2
    - the percent incorrect of upgrades for benign masses from IUS BI-RADS 2-3 to Imagio (IUS+OA) BI-RADS 4-5 and from IUS BI-RADS 2 to Imagio (IUS+OA) BI-RADS 3-4-5
    - the percent of incorrect downgrades for malignant masses from IUS BI-RADS 4-5 to Imagio (IUS+OA) BI-RADS 2-3; and
    - the percent of correct upgrades for malignant masses from IUS BI-RADS 2-3 to Imagio (IUS+OA) BI-RADS 4-5.
2. the Cumulative effect of downgrades and upgrades for combined benign masses and malignant masses.
3. the SenoGram usage:
  - Utilization percent reported by the readers
  - Sensitivity and specificity discordance with Imagio (IUS+OA) Downgrades and upgrades versus Imagio (IUS+OA) and IUS, separately for benign and malignant masses
  - POM paired differences versus Imagio (IUS+OA) and IUS, separately for benign and malignant masses.
4. the SenoGram performance:
  - Sensitivity and specificity compared to sensitivity and specificity estimated from cross-validation and hold-out validation.
  - Partial AUC for individual users and overall corresponding to 95-99% sensitivity
  - Separate assessment of Senogram performance with and without mammographic data input.

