- Comprising the 155 mass read sets, the first cohort will consist of 75 benign and 45 malignant masses (reflecting the same 37.5% prevalence of cancer as for the overall pivotal ITD population), classified by conventional diagnostic ultrasound (CDU) as BI-RADS 3 to 5 to be selected at random in proportion to the original assignment distribution of BI-RADS classifications among subjects in the PIONEER Study. To facilitate the alignment of the PIONEER Pivotal Study data with the Feasibility Study data, the mass image set sampling plan will select a proportion with and without mammograms depending on availability of the mammograms, separately for benign and malignant masses. Cohort 1 will be used for the effectiveness endpoint analyses in support of decision making. The same sampling strategy will be used to ensure a comparable proportion of mass image sets as for the PIONEER Pivotal Study.

- The second cohort consists of 30 additional malignant masses for which 1 or more pivotal study readers scored the mass a false negative during a read from the PIONEER study; this will assess if the excess FN rate observed with OA in the PIONEER study can be reversed.
- The third cohort will consist of five DCIS, lymphoma, or Phyllodes masses; this will assess how these atypical cases will be scored. Since there are so few of these cases, mammogram matching will not be possible.

This evaluation will further achieve the following:

1. The incremental contributions of IUS and Imagio (IUS+OA) by assessing the BI-RADS and POM values at each step in the read order traditionally used in clinical practice.
2. The SenoGram performance versus IUS and versus Imagio (IUS+OA) once IUS + OA features are scored with subset evaluation of the effect of presence or absence of the mammographic data on Senogram performance.

The SenoGram is a classification model that predicts the probability that a lesion is malignant for a given set of reader-assigned feature scores and other relevant data. For this study, the SenoGram will consist of two components, a user interface and a back-end computation engine. The reader will enter feature data into the user interface. When all data has been entered, but prior to a final submission of the data, the user interface will graphically display the model's predicted likelihood of malignancy [not to be confused with POM].

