## 9. STATISTICAL CONSIDERATIONS

### 9.1 General Design Issues

BBRF will implement the Feasibility Study sampling plan to represent the PIONEER Pivotal Study masses to reflect mammography use and site CDU BI-RADS score.

BBRF will determine which masses are to be assigned to each cohort; Cohorts 1-3 will be the same across all readers.

The unit of measurement for reader-based outcomes is at the reader-mass level. The Feasibility Study will be used to assess if independent readers can conduct pre-specified POM evaluations separately for IUS and then for Imagio (IUS+OA) and the Senogram to evaluate the primary and secondary effectiveness endpoints. Pre-specified POM evaluations will be performed separately for IUS, Imagio (IUS+OA), and the reader use of the SenoGram to evaluate the Imagio (IUS+OA) and SenoGram specificities and sensitivities.

The primary endpoint is to show a specificity advantage for fixed sensitivity; this diffuses the tradeoff between FNs and FPs if the FN rate is the same. These sensitivity and specificities will be calculated overall and per reader using generalized estimating equations (GEE) and the analysis of variance (ANOVA) modeling as well as for observed without adjustment.

For each endpoint, Imagio will be compared versus IUS; the same analyses will be performed for the SenoGram versus IUS and Imagio.

The specificity advantages will be computed for fixed sensitivity (e.g. 98% target) with interpolation or extrapolation used by calculating the specificities and sensitivities from the ROC curve as needed. This same principle will be used to construct the partial ROC curves and to compute the area under the ROC curve to correspond to 95-99% sensitivity.

The results from the Feasibility Study will be used to judge if there is sufficient rationale to proceed to a pivotal study involving more masses and more readers to support the indications for use. If there is sufficient strength of the data, then the Imagio Feasibility Study results will be used to determine the pivotal study sample size. The effect sizes will be assessed to judge if the pivotal study can be conducted with at least 80% power for two-sided hypothesis testing with 5% Type I error; this depends on the effect sizes achieved for the primary and secondary effectiveness endpoints as well as inter-reader variabilities.

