#### 1. Sensitivity, Specificity, Partial ROC AUC, and Specificity for Fixed Sensitivity

Individual reader specificity and sensitivity will be calculated from simple counts for POMs to construct the respective ROC curves for IUS, the Imagio (IUS+OA) and the SenoGram. GEE and ANOVA will be used to describe overall specificity and sensitivity as well as to compute the two-sided 95% confidence intervals for the OA-IUS differences for sensitivity and for specificity.

The specificity advantage for fixed sensitivity will be the primary endpoint. It will be computed from the respective ROC curves which are generated according to the POMs corresponding to the 95-99% sensitivity range. To compute the specificity advantage for fixed sensitivity, interpolation may be required; a fixed sensitivity will be targeted, e.g., 98%. To compute the specificity advantage and the partial area under the ROC, the specificities and sensitivities may need to be further computed from the ROC curves as needed. The McClish method will be used to analyze and compare the partial ROC curves. The variances will be computed to construct the two-sided 95% CIs for Imagio (IUS+OA), IUS, and for the Imagio (IUS+OA) -IUS difference. The same analyses will be performed for the SenoGram versus IUS and versus Imagio (IUS+OA).

In addition, the interpolation and the corresponding variance estimate will also permit the calculation of the specificity difference for fixed sensitivity (e.g. 98%) as well as the two-sided 95% confidence interval for the difference.

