**Table 3: Correct Upgrades and Incorrect Downgrades**

Imagio (IUS+OA) Outcome (IUS→Imagio)	Malignant Masses
BR2→BR4-5	% (IC4-5/IC2)
BR3→BR4-5	% (IC4-5/IC3)
Correct Upgrades	% (ICN/ICD)
Imagio (IUS+OA) Outcome (IUS→Imagio)	Malignant Masses
BR4->BR2-3	% (IC2-3/IC4)
BR5->BR2-3	% (IC2-3/IC5)
Incorrect Downgrades	% (ICN/ICD)

To assess the cumulative effect of downgrades and upgrades for combined benign masses and malignant masses, a net gain will be computed for downgrades and upgrades. The net gain will be computed in SAS according to contrast statements for the ANOVA models to simultaneously analyze reader and mass. The weight (W) of the malignant outcomes (TP and FN) will be computed to determine the value  $(A-B+W(C-D))$  that achieves statistical significance. The same analyses will be performed for the SenoGram versus IUS and versus Imagio. Refer to Table 4 below.

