### 4. NLR

The NLR  $((1-\text{sensitivity})/\text{specificity})$  will be computed using the standard formula with two-sided 95% CIs computed using exact 2x2 contingency table methods. A two-sided 95% CI for the NLR  $<1$  and favoring OA will indicate improvement in NLR; the relative NLR will also be computed relative to IUS. The same analysis will be performed for SenoGram versus IUS and versus Imagio (IUS+OA).

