
BI-RADS (BR): Downgrade (IUS+OA post) defined as:
 
 • IUS in BR 4a and IUS+OA post in BR 2-3 or • IUS in BR 3 and IUS+OA post in BR 2 
BI-RADS: Upgrade defined as:
 
 • IUS in BR 2 and IUS+OA post in BR 3-5 or • IUS in BR 3 and IUS+OA post in BR 4-5 
Tables will be repeated for IUS x IUS+OA post, IUS vs IUS+OA pre and IUS+OA pre vs IUS+OA post.
	
SAS: BI-RADS Grade Changes (Grouped BI-RADS), simple counts with 95% CI.
 
Benign+TPB: Reference PIONEER Table 14.2.13.4 [t_14_02_13_birch1_04]
 
Cancers: Reference PIONEER Table 14.2.13.7 [t_14_02_13_birch2_07]
 
Note: change from 99% CI to 95% CI

Net grade change – All masses – weight (W) that results in a significant OA+IUS vs IUS reflecting the FP advantage minus the weighted FN disadvantage.
	
SAS: PROC GENMOD and MIXED linear models will contrast difference in FN and FP to demonstrate clinical benefit.
 
Tables to be repeated for IUS x IUS+OA post, IUS vs IUS+OA pre and IUS+OA pre vs IUS+OA post

SenoGram performance using the following metrics from the study endpoints:
 
a) Sensitivity and specificity for SenoGram classification based on predicted probability and the SenoGram threshold, with separate analysis for each study cohort and with subgroup analysis for masses with and without mammogram BI-RADS data.
	
For each metric, a summary table for each reader (where appropriate) and for all readers to contain the following:
 
 • Measured value using Reader-01 feature data. • Estimated value from SenoGram cross-validation with PIONEER feature data. • Estimated value from SenoGram predictions for cohort masses with

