1.1.7.2. Evaluating the SenoGram

SenoGram evaluation is divided into: 1) evaluation of reader utilization, and 2) correctness of the SenoGram prediction. Evaluation of reader utilization includes the following analysis:

- IUS+OA post vs IUS+OA pre-as described in Table 1 - Cohort 1: Primary and Cohort 1: Secondary.
- N (%) masses with reader reporting use of the SenoGram.
- N (%) masses with reader reporting that SenoGram increased their confidence in their assigned BI-RADs category.
- N (%) masses with reader reporting that SenoGram decreased their confidence in their assigned BI-RADs category.

Evaluation of correctness of SenoGram predictions will be based on the analysis listed in Table 1.

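### The protocol's SenoGram comparisons survive in the SAP only through reader scores: the model's own output has no paired contrast with IUS or Imagio and no discordance table, and the change is undeclared

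*SAP*

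**What the plan says.** **Protocol.** Section 4 lists, among what the study will achieve, "The SenoGram performance versus IUS and versus Imagio (IUS+OA) once IUS + OA features are scored". Section 9.1 extends this to every endpoint: "the same analyses will be performed for the SenoGram versus IUS and Imagio". The promise is repeated in the opening of 9.8 and in 9.8 items 1 (ROC measures), 2 (net gain: "The same analyses will be performed for the SenoGram versus IUS and versus Imagio"), 3 (move-forward criteria) and 4 (NLR). Under SenoGram usage, Section 2.2 item 3 lists discordance with Imagio, upgrades and downgrades, and "POM paired differences versus Imagio (IUS+OA) and IUS, separately for benign and malignant masses". Section 1.2 states the purpose: SenoGram usage and performance are to inform whether the model is adjusted before the pivotal study.

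**SAP.** Table 1 and 1.1.7.1 use three pairwise contrasts: IUS+OA post versus IUS, IUS+OA pre versus IUS, and post versus pre. SAP 1.1.7 defines the post score as what the reader enters after viewing the SenoGram. The model's own output appears in the SenoGram performance rows of Table 1. There its value on this study's reader features is shown with "Estimated value from SenoGram cross-validation with PIONEER feature data" and with predictions for the cohort masses from PIONEER data. SAP 1.1.7.2 adds: "Evaluation of correctness of SenoGram predictions will be based on the analysis listed in Table 1". SAP Section 2, on changes to the planned analyses, mentions only the mammogram sampling.

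**The concern.** The protocol treats the SenoGram as something to be compared with the readers. The SAP compares the model only with other runs of the model, and compares readers only with readers. If post-SenoGram performance disappoints, the sponsor will want to know whether the model trailed the readers or whether readers set aside good predictions, since the two call for different action before the pivotal study. The direct evidence would be a paired model-minus-reader difference with an interval, and a table of disagreements against truth. Neither is planned, although the protocol calls for SenoGram comparisons and names discordance as an endpoint.

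**Working it through.** The documents give no figure to reproduce, so the check is mainly a comparison of texts.

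**Step 1: which SenoGram is meant.** The protocol uses the word in two senses.
- *Model output.* Section 4 defines the SenoGram as a classification model and warns against confusing its likelihood with POM. Section 9.8 item 1 builds separate ROC curves for IUS, Imagio and the SenoGram. Item 5 separates POM for Imagio from the SenoGram's likelihood.
- *Reader's score.* One sentence in 9.1 speaks of the reader's use of the SenoGram. But Section 4 labels the post-SenoGram score an Imagio score.

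**Step 2: what the SAP provides under each sense.**

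| Protocol analysis | Model output | Reader's post-SenoGram score |
|---|---|---|
| Specificity at fixed sensitivity; partial AUC | values only, no difference or CI against readers | post vs IUS, post vs pre |
| Sensitivity and specificity | values at the SenoGram threshold, no difference against readers | differences with 95% CIs, 2% POM cutoff |
| Upgrades and downgrades | none | post vs IUS, pre vs post, by diagnosis |
| POM paired differences | none | three pairwise differences by diagnosis (1.1.7.1) |
| Net gain | none | all three contrasts |
| NLR | none | IUS and post only; pre not named |
| Discordance | none | none |

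Contrasts of model output with IUS or Imagio: 0. Reader-score contrasts: 3, of which 2 (post vs IUS, post vs pre) carry the model's effect through the reader.

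**Step 3: what a side-by-side reading loses in precision.** This is an illustration. The 75 benign Cohort 1 masses come from the documents. Assumed are one reader, specificities p1 = 0.30 to 0.50 and p2 = p1 + 0.10, and within-mass correlation ρ. The Wald half-width is

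1.96 × √{[p1(1−p1) + p2(1−p2) − 2ρ√(p1(1−p1)p2(1−p2))] / 75}.

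For p1 = 0.40 and p2 = 0.50:
- ρ = 0, as if independent: 1.96 × √(0.49/75) = 0.158.
- ρ = 0.5: 1.96 × √((0.49 − 0.245)/75) = 0.112.

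Over the whole assumed range the half-width is:
- 0.152 to 0.158 at ρ = 0
- 0.127 to 0.133 at ρ = 0.3
- 0.107 to 0.112 at ρ = 0.5
- 0.083 to 0.087 at ρ = 0.7

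This treats specificity as a simple proportion at a set cutoff. It ignores interpolation to 98% sensitivity and averaging over readers. Without the pairing, precision is lost but the information is not removed.

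**Step 4: what marginal values cannot show.** Suppose, as an assumption, that model and reader each have 40% specificity, so 0.40 × 75 = 30 benign masses correct for each. Disagreements number 60 − 2 × overlap, and the overlap can be anything from 0 to 30. The same two marginal figures therefore fit anywhere from 0 to 60 disagreements. Only a cross-tabulation by mass shows how many there were and who was right.

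**The case against.** A reader might infer that the SAP drops every SenoGram comparison. The documents do not support that. On the reader's-use sense in Protocol 9.1, post versus IUS and post versus pre are the promised contrasts. Protocol 2.2 item 3 is headed usage, with model performance left to item 4, so its POM differences and upgrades and downgrades can fairly be read as reader scores. The SAP covers both by diagnosis. Of the three item 3 comparisons, only discordance has no counterpart on either reading.

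A reader might also infer that the study could not tell whether the model or the readers need changing. That goes too far. Reader-01 features against PIONEER data on the same masses bear on feature scoring. The measured value against cross-validation bears on the model. Post versus pre, with reported use and confidence, bears on uptake. Specificity at 98% sensitivity and partial AUC are reported for model and readers on the same Cohort 1 masses. The cross-validation row is not itself a fault, because Protocol 2.2 item 4 asks for that comparator.

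Nor does the protocol attach intervals to every SenoGram contrast. The opening of 9.8 and its items 1 and 4 do so by reference, while Section 4, 9.1, net gain and the move-forward criteria do not. The study is also descriptive and unpowered, which limits the cost of a missing interval.

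All of this stands, and it narrows the point without removing it. The weight of the protocol favours the model-output sense. Sensitivity and specificity are not like for like, since the model is judged at its own threshold and readers at a 2% POM cutoff. Post versus pre shows whether readers moved, not whether the model was right when they did not.

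**Conclusion.** The point holds in limited form. For the model's own output, the SAP plans no paired difference or interval against IUS or the pre-SenoGram read, no NLR, no net gain and no discordance table. Section 2 does not declare this. Nothing planned shows with stated precision whether the model alone beats or trails the readers, or whether readers overrode correct predictions. Both matter to the Protocol 1.2 decision on adjusting the model.

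The primary endpoint is untouched and a descriptive side-by-side remains possible, so this is a should-fix alignment of SAP with protocol. The conclusion rests on reading SenoGram as model output. On the other reading the gap shrinks to discordance and the pre-SenoGram NLR. The half-widths and the disagreement range rest on assumed specificities and correlations and show direction only.

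**What to change.** - In SAP Table 1 and 1.1.7.2, define SenoGram as the model output, distinct from IUS+OA post.
- Enter the predicted likelihood for each reader and mass as a further modality in the Cohort 1 analyses of specificity at 98% sensitivity and partial AUC. Report SenoGram minus IUS and SenoGram minus IUS+OA pre with 95% CIs. SenoGram minus IUS+OA post is optional, as the protocol does not single it out.
- Add a table of reader/SenoGram disagreements, separately for benign and malignant masses, showing which was correct.
- List in SAP Section 2, with reasons, any protocol SenoGram contrast that is still not analysed.

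The cost is SAP wording and a few descriptive tables. The documents do not say that each displayed prediction is stored, but Table 1 already requires SenoGram values from this study's reader features, so no new reads are needed.

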1.1.7.1. Feasibility Analysis Methodology

Data Analyses

Hypotheses generating analyses will be based on independent readers for POM, BI-RADS and feature scores (IUS, IUS+OA pre, IUS+OA post) individually and overall. There are no formal hypothesis tests; p-values from all analyses are descriptive only. There are no adjustments for multiple testing. There will be no adjustment in p-values reported for the planned interim analysis after a minimum of 72 reads by each reader in Cohort 1. Truth (determination of malignant biopsy, benign biopsy, or TPB) will be taken from PIONEER.

The analyses below will be done for Cohort 1, repeated for malignant masses only for cohort 2. No summaries (listings only) will be done for the 5 masses in Cohort 3.

The specificity advantage of IUS+OA post vs IUS, IUS+OA pre vs IUS and IUS+OA post vs IUS+OA pre will be compared at fixed 98% sensitivity. The software package OR-DBM MRMC [Version 2.5 or later] will be used for this analysis of OA gain as interpolated from the ROC curves.

Specificity and sensitivity will be calculated by reader and overall for IUS, IUS+OA pre, IUS+OA post, and the 3 pairwise differences [PROC GENMOD, readers as independent,

repeated as masses as independent]. Specificity and sensitivity will be calculated (not model-adjusted) using the 2% POM cutoff for IUS+OA pre, IUS+OA post and IUS; and then for robustness analyses, for 1%, 3%, 4%, and 5% cutoffs.

Clinically relevant up and downgrades based on BI-RADs are defined as:

- Downgrades: IUS in BR 4a and IUS+OA post in BR 2-3 or IUS in BR 3 and IUS+OA post in BR 2
- Upgrades: IUS in BR 2 and IUS+OA post in BR 3-5 or IUS in BR 3 and IUS+OA post in BR 4-5.

These definitions likewise hold for differences for IUS vs IUS+OA pre and IUS+OA pre and IUS+OA post. These clinically relevant up and downgrades will be reported by reader and overall for benign and cancers separately. For benign masses, up and downgrades will be reported for masses with and without mammograms.

To assess the net effect of downgrades and upgrades, a net gain will be computed in SAS using contrast statements for the ANOVA to determine weight (W) of the malignant outcomes (TP and FN) to determine the value $(A-B+W(C-D))$ that achieves statistical significance, where A, B, C and D are defined as:

- A. Benign Masses correctly downgraded using IUS+OA post
- B. Benign Masses incorrectly upgraded using IUS+OA post
- C. Malignant masses correctly upgraded using IUS+OA post
- D. Malignant masses incorrectly downgraded using IUS+OA post

These analyses will be repeated for IUS vs IUS+OA pre, IUS vs IUS+OA post and IUS+OA pre vs IUS+OA post.

The sample size for a pivotal study will be calculated using method implemented in the MRMC Sample Size Program 1.0 for Diagnostic Studies, by Hillis, Obuchowski, and Birnbaum [7]. These sample size results may be confirmed by other packages such as nQuery, PASS, and SAS [PROC POWER].

POM summary statistics for IUS, IUS+OA pre and IUS+OA post, and the 3 pairwise differences will be displayed by diagnostic category and compared using a Wilcoxon statistic. POM scores for benign masses will be displayed for masses with and without mammograms.

OA feature scores including internal total, external total, and overall total scores will be summarized to describe the distribution of individual feature scores by diagnosis, with a Wilcoxon statistical test for the difference in the distributions between malignant and benign. Feature scores for benign masses will be displayed for masses with and without mammograms.

